7.4 Emergency Unblinding

If it is deemed necessary by the clinical or research team to unblind the patient to the allocated treatment the CI must be contacted. Only the CI or delegated individual on the delegation log can decide to unblind. Emergency unblinding will be available to the investigator / pharmacist / Sponsor via the web based Sealed Envelope system. The username and password will be tested in advance of the first patient enrolled onto the trial. The Sealed Envelope system will be fully audit traceable until the end of the trial to ensure that blinding has not been compromised. Unblinding will only occur in the case of a medical emergency or if a patient experiences an unexpected serious reaction such as a SUSAR.

Unblinding of all subjects will take place when the last patient has had their final visit assessments and data collection and validation is complete.

To test the validity of the blinding both the patients and researchers will be asked if they were aware of treatment allocation.

Unblinding before database lock must only be used in an emergency situation when the identity of the trial drug must be known to the Investigator in order to provide appropriate medical treatment or otherwise assure safety of trial participants. The reason for unblinding must be documented in the source documents and recorded on the web based randomisation system when unblinding along with the date and the initials of the person who broke the code. Reason for unblinding should also be recorded in the CRF, data collection tool, in the site file and medical notes. In the case of unblinding an individual participant for safety reasons, appropriate follow-up of safety related events is required. It will also be documented at the end of the trial in any final trial report and/or statistical report. The Cl/Investigating team will notify the Sponsor and the LCTU in writing as soon as possible following the unblinding detailing the necessity.

7.5 The randomisation scheme

The LCTU will supply a web based randomisation system from a third party (Sealed Envelope Ltd.). Participants will be randomised in a 1:1 ratio to anti-ST2 or placebo, this will be set up as a blinded randomisation process. Each participant will be given a unique screening number on consent, and a unique participant ID when they are randomised. This combination of unique screening number and participant ID will be linked on the enrolment log with the unique participant ID number being used to identify the individual participant throughout the trial following randomisation. Neither of these numbers will be re-assigned to any other subject. Participants will be assigned to trial treatment in accordance with the randomisation schedule.

Randomisation will be stratified by frequency of exacerbation in the previous 12 months (Low [2 or 3] or High [4 or more]). Randomisation results will be printed out and signed as confirmation by the unblinded trial personnel performing the randomisation and a copy will be stored securely with the unblinded documentation and presented to pharmacy alongside the prescription.

7.5.1 Method of implementing the randomisation/allocation sequence

Once the participant has given written consent to the trial, a member of the trial team will assess the eligibility of the participant by completing a screening visit. If eligible, randomisation should occur immediately after the participant undergoes their baseline assessment where possible. The unblinded trial personnel (authorised and trained) will complete a randomisation form, enter the eligibility criteria data onto the online system and randomise the participant to a treatment allocation, this will generate a unique participant ID and a blinded randomisation code which relates either to the IMP (anti-ST2 or placebo). The linkage information between the randomisation code list(s) and the allocated treatment will be generated/held by the Sealed Envelope system and by the unblinded trial personnel.

7.6 Baseline data

See Appendix 1 for detailed visit structure and trial procedures.

7.7 Trial assessments

See Appendix 1 for detailed visit structure and trial procedures. For dosage schedules please see section 8.6. For Trial restrictions and missed windows please see Section 8.10.

7.8 Long term follow-up assessments

See Appendix 1 for detailed visit structure and trial procedures.

7.9 Qualitative assessments

There will be no qualitative assessment.

7.10 Withdrawal criteria

The only specified withdrawal criteria for this study will be for participants that miss more than one dose of the study treatment, or who delay a scheduled study visit for >4 weeks. These participants will remain in follow-up for the trial duration. If a participant wishes to completely withdraw from the study, or is withdrawn for reasons other than a missed or delayed dose, the research team will encourage them to undertake the 'withdrawal visit' procedures and assessments which will signify the end of their participation. This will include participants who withdraw via telephone. It will be at the participant's discretion whether or not they attend the withdrawal visit. Withdrawal visits should be completed as soon as possible, however the timeframe will be largely dependent on what the participants finds acceptable.

Every effort should be made by the research team to keep the participants in the trial. However, participants have the right to withdraw their consent to take part in the trial at any time without having to give a reason and this will not affect their future care. Withdrawal details and reasons (if known) should be recorded on the withdrawal/loss to follow up CRF and in the medical notes. In addition, the investigator may discontinue a participant from the trial at any time if the investigator considers it necessary. The IMP will also be discontinued in the case of an adverse event which the investigator considers sufficient to jeopardise the safety of the trial participant. Participants who want to discontinue protocolled treatment should be encouraged to remain in the trial and continue to be followed-up as per protocol or as of routine care.

Every effort should be made to keep the participant in the trial to collect important efficacy and safety data. Withdrawals from the trial should be discussed with the CI or their deputy and the Trial Manager. If a participant has withdrawn from the trial for any reason, then his/her screening and participant ID number(s) cannot be issued to another participant.

Loss to follow-up will be minimised by diligent liaison with the participant, their medical team and if required the general practitioner. If a participant fails to attend the clinic for trial visit, the research team should contact the participant and re-schedule the missed visit within a week. If the participant can't be contacted or misses his/her next appointment, the research team should make every effort to contact the participant again by phone and letter. If the participant still cannot be contacted, then he/she can be withdrawn from the trial and the reason in the notes and eCRF can be recorded as 'lost to follow-up'.

A participant will be considered to have completed the trial if:

- they continue to take trial treatment until Visit 12 (Week 44) and attend Visit 14 (Week 60)
- they continue to participate in the trial until Visit 13 (Week 48) regardless of whether they continue to take IP.

As stated in section 3.3.2, participants will undergo a non-contrast CT scan at the beginning and end of the trial. Bearing in mind the average age of participants, diagnosis of COPD and smoking history, lung nodules are a very common finding in this population. Therefore participants will remain in the trial whilst they are followed up in the virtual nodule clinic, however

at the point where a suspicious nodule has led them into the cancer pathway, they will be withdrawn from the trial.

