6.2 Exclusion criteria

- 1. Significant known respiratory disorders other than COPD that in the view of the investigator will affect the trial
- 2. Patients whose treatment is considered palliative (life expectancy <12 months)
- 3. Known hypersensitivity to the active substance of IMP or any of the excipients
- 4. Known history of anaphylaxis
- 5. Patients with a COPD exacerbation and/or pneumonia within the 4 weeks prior to visit 1
- 6. Have, in the opinion of investigator, uncontrolled co-morbid conditions, such as diabetes mellitus, hypertension and heart failure [e.g. NYHA class III (e.g. less than ordinary activity causes fatigue, palpitation, or dyspnoea) patients will be excluded if they have had exacerbation of their HF in previous 6 months, and class IV (e.g. Symptoms of heart failure at rest)] that will affect the trial.
- 7. Myocardial infarction, unstable angina or stroke within 12 month prior to screening
- 8. Diagnosis of malignancy within 5 years of visit 1 (except for excised localised carcinoma of skin not including malignant melanoma)
- 9. Clinically significant ECG changes, which in the opinion of investigator warrants further investigations
- 10. Laboratory abnormalities, which in the opinion of investigator warrants further investigations
- 11. Have, in the opinion of the investigator, evidence of alcohol, drug or solvent abuse.
- 12. Pregnant, breastfeeding, or lactating women. Women of child-bearing potential (see protocol section 9.7)) must have a negative blood serum pregnancy test performed at the screening visit and must agree to use two methods of birth control, (one of which must be a barrier method).
- 13. Participation in an interventional clinical trial within 3 months of visit 1 or receipt of any investigational medicinal product within 3 months or 5 half-lives.
- 14. Upon questioning the patient has blood born infection (e.g. HIV, hepatitis B or C).

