8.7 Dosage modifications

There will not be any dose modification during the trial (see Section 8.10 for non IMP medication changes).

If a participant has an anaphylactic reaction to the drug or placebo, they will discontinue from protocolled treatment but remain in follow-up. If the drug was stopped due to a clinical reason such as allergic reaction, we will err on side of caution and not restart the drug in the same participant.

No information on overdose, maximum-tolerated dose, or dose-limiting toxicities has been established at this time.

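### Protocol 7.10 withdraws cancer-pathway participants from the trial, not only from study drug, so their later exacerbations to week 48 are not systematically collected; the effect is small and the fix cheap

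*Protocol*

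**What the plan says.** Protocol 7.10 notes that "lung nodules are a very common finding in this population" and keeps participants in the trial while the virtual nodule clinic follows them. After that, "at the point where a suspicious nodule has led them into the cancer pathway, they will be withdrawn from the trial". The section does not separate stopping study drug from stopping data collection.

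Earlier in 7.10, a person withdrawn for anything other than a missed or delayed dose is encouraged to attend a withdrawal visit, with "procedures and assessments which will signify the end of their participation". In the schedule of procedures (Protocol Appendix 1 and SAP Table 1), the exacerbation-frequency row carries no mark in the withdrawal column. SAP 3.2 keeps all randomised participants in the ITT set but takes data from early withdrawals only up to the point of discontinuation.

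Other rules for stopping treatment differ:

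- **More than one missed dose, or a visit delayed by over four weeks (7.10):** the participant stays in follow-up until the trial ends.
- **Anaphylaxis (8.7):** "they will discontinue from protocolled treatment but remain in follow-up".
- **Own wish to stop (7.10):** "Participants who want to discontinue protocolled treatment should be encouraged to remain in the trial and continue to be followed-up as per protocol".
- **General aim (7.10):** "Every effort should be made to keep the participant in the trial to collect important efficacy and safety data".
- **One of the two definitions of completion (7.10):** "they continue to participate in the trial until Visit 13 (Week 48) regardless of whether they continue to take IP".

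**The concern.** An intention-to-treat comparison over 48 weeks needs exacerbation counts to week 48 for everyone randomised, on or off drug. Here a protocol rule, rather than the participant's choice, cuts off that collection. CT is done at screening, so a nodule can be known before the first dose and lead to a cancer referral inside the primary window.

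The clinical reason for stopping drug is clear. The exclusion criteria rule out a "Diagnosis of malignancy within 5 years of visit 1" (apart from excised localised skin carcinoma), and the antibody's safety profile is not fully known. Neither is a reason to stop counting exacerbations.

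At stake are avoidable gaps in the primary outcome and more weight on the missing-at-random assumption. That assumption is least comfortable for people who leave because of a suspected new lung disease.

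**Working it through.** **What is collected after withdrawal.** Four routes could pick up later events.

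| Route | Limit |
|---|---|
| SAE reporting, to 100 days after early cessation (Protocol 9.3) | 9.1 does not count COPD exacerbations as adverse events unless judged drug-related. 9.2.1 says expected serious disease events are reported as SAEs and may also be captured as exacerbations. Hospitalised events may surface; community steroid or antibiotic courses would not. |
| Death notification (9.5) | Fatal events only. |
| Primary and secondary care record extraction (11.1) | A permission to be requested; not described as outcome collection after withdrawal. |
| GP contact (11.2) | Only if required. |

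None is set up to count moderate exacerbations to week 48, and SAP 3.2 would not use them.

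**When the rule bites.** It affects the primary outcome only if pathway entry precedes week 48. A nodule first seen on the week-48 CT costs nothing.

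**Person-time.** Planned total: 80 × 48 = 3,840 weeks. An exit at week w loses 48 − w.

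- w = 12: 36/3,840 = 0.94%
- w = 24: 24/3,840 = 0.63%
- w = 36: 12/3,840 = 0.31%
- Ceiling, exit at randomisation: 48/3,840 = 1.25%
- Four exits at week 12: 144/3,840 = 3.75%

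**Events.** Protocol 10.1 assumes placebo rates of 2.0 or 2.5 per year with reductions of 50% or 40%, so anti-ST2 rates are 2.0 × 0.5 = 1.0 or 2.5 × 0.6 = 1.5. One exit at week 12 leaves between 36/52 × 1.0 = 0.69 and 36/52 × 2.5 = 1.73 expected exacerbations unrecorded.

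**Power: the plan's own figure.** The plan states 80% with 80 recruited and 10% drop-out, that is 36 per arm. I used a two-sided 5% Wald test of the log rate ratio with variance 1/I₀ + 1/I₁. Each participant contributes μ/(1 + kμ) to the information, or μ/1.3 if 1.3 is a variance-to-mean ratio, with μ = rate × weeks/52. The documents do not say which meaning of 1.3 is intended.

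| Reading of 1.3 | 2.0 v 1.0 per year | 2.5 v 1.5 per year |
|---|---|---|
| k = 1.3 | 52.5% | 35.3% |
| k = 1/1.3 | 64.7% | 46.3% |
| variance/mean = 1.3 | 81.6% | 70.6% |

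Only one of the six cells is close to 80%. That is a separate matter; here only the change in power is used, over all three readings.

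**Power: change due to the rule.** The largest case is variance/mean = 1.3, 2.5 v 1.5 per year, 36 per arm.

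- No exits: I₀ = 36 × 2.308/1.3 = 63.91 and I₁ = 36 × 1.385/1.3 = 38.34. SE = √(1/63.91 + 1/38.34) = 0.2043. Power = Φ(0.5108/0.2043 − 1.96) = 70.6%.
- Two per arm leaving at week 12: each contributes a quarter of its information, so each arm keeps 34.5/36. I₀ = 61.24, I₁ = 36.75, SE = 0.2087, power = 68.7%.
- Loss: 1.84 points.

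Over all three readings, both scenarios and 36 or 40 per arm, one week-12 exit per arm costs 0.38 to 0.91 points and two per arm cost 0.76 to 1.84. With exits at week 24, two per arm cost at most 1.22 points.

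**Bias.** The documents give no count, timing or later exacerbation rate for such participants, so neither size nor direction can be computed. A deliberately extreme illustration puts four of 40 in the active arm only, all leaving halfway, with their rate tripled afterwards. The full-follow-up arm rate rises by 4/40 × 0.5 × (3 − 1) = 10%, so a rate ratio of 0.50 becomes 0.55, or 0.60 becomes 0.66.

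**The case against.** The strongest reply is that the plan already handles this. SAP 5.4.1 uses log-time on study as an offset, SAP 5.4.3 adds controlled multiple imputation for departures from missing at random, and four exits would be only half of the 8 drop-outs allowed for (10% of 80). This stands as mitigation. But imputation models the missing events and does not observe them, and the drop-out allowance protects power, not the missing-data assumption.

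Four further objections stand in part.

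- A reader might infer that every later event is lost. The documents do not support that: the routes tabulated above could catch some hospitalised or fatal events, and some others from records.
- A reader might infer that the rule contradicts the rest of 7.10. It does not, strictly. The retention text is a general aim, the completion definition only classifies participants, the stay-in route is for people who want to stop drug, and the same section lets the investigator discontinue a participant. A specific rule may differ; the criticism is that no reason is given for ending outcome collection.
- Participants stay in during nodule surveillance, so exits would probably come later than week 12 and cost less. The week-12 figures sit near the upper end.
- The outcome requires symptomatic worsening of COPD, so courses given during cancer investigation may be misclassified. That limits the value of the recovered data.

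**Conclusion.** The point holds as a small, avoidable weakness. The rule ends participation where stopping drug would be enough, and no procedure systematically collects the later moderate-to-severe exacerbations that the 48-week intention-to-treat analysis needs.

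Each exit at week 12 or later loses less than 1% of planned person-time, and up to four exits at week 12 cost at most about 1.8 power points. These sizes rest on an assumed number and timing of exits, on the planning rates, and on three readings of the over-dispersion figure.

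It would be tempting to read this as bias in the treatment comparison. The documents do not show that: the trial is double-blind, and the nodules that matter come mainly from a CT taken before randomisation. The rate-ratio illustration shows only what an extreme imbalance would do; nothing suggests that it occurred.

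**What to change.** In Protocol 7.10, state that a participant who enters the cancer pathway stops study drug but, unless consent is withdrawn, exacerbation and safety data continue to be collected to week 48 by telephone or from GP and hospital records. State also that these data enter the ITT analysis, with time on study counted to the end of that follow-up. SAP 3.2 then needs no change, because such a participant has not discontinued the study.

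An optional tidy-up is SAP 5.4.1, which explains the offset as time on treatment although the specified term is time on study. The operative wording is already right.

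The cost is one protocol sentence with the approvals in Protocol 13.12, a few extra contacts with people under cancer investigation, and some steroid or antibiotic courses that are harder to attribute to COPD. Telephone follow-up was already in use under the COVID-19 provisions.

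Timing limits the gain in this trial. The amendment history shows recruitment complete by 11 September 2019; 48 weeks later is about 12 August 2020, before protocol version 7.0 was issued on 11 September 2020. Most recoverable data would therefore come from record extraction, where consent covers it.

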7.11 Storage and analysis of clinical samples

See Appendix 1 and trial procedures and laboratory manual for standard operating procedures (SOPs).

The following blood samples will be processed by the University Hospitals of Leicester NHS Trust central pathology labs and will be collected at room temperature from the trial site:

- Biochemistry Profile Full (including U&E,s LFTs)
- Full Blood Count (FBC/CBC)
- NTproBNP
- HbA1c
- Lipid profile
- Total IgE
- RAST (HDM, Cat ,dog, grass pollen)
- C-Reactive Protein

The following samples will be analysed for research purposes by the research team and processed at the Respiratory BRC laboratories. Samples will be kept on ice or stored in monitored -20C or -80C freezers prior to analysis, unless contraindicated.

- Urine sample (for inflammatory biomarkers and pregnancy)
- Sputum sample (Sputum is collected on ice and processed at 4°C as soon as possible and within 2 hours of expectoration)
- Nasal epithelial sample (optional)
- Nasosorption
- PK and ADA samples
- Serum Plasma (for inflammatory biomarkers)
- Pregnancy Testing (blood sample)
- DNA sample
- RNA sample

The DNA and RNA samples taken during this study will be stored in a -80C temperature monitored freezer in the Respiratory BRC, all analysis on these samples will be carried out at the end of the study. The Respiratory BRC is a registered Tissue Bank.

7.12 End of trial (ET)

The end of the trial is defined as the last participant's final visit.

However, final trial closure will be when all final sample analysis has been completed or at the discretion of the TSC acting on the recommendation of the DSMC. Participants who discontinue the trial early will be asked to return to the trial centre and will undergo withdrawal or early

termination (ET) visit procedures listed in Appendix 1 under 'withdrawal'. The withdrawal visit will include all procedures to be done at end of trial visit as well as any other laboratory assessment planned at the originally scheduled follow-up visit.

8 TRIAL TREATMENTS

8.1 Name and description of investigational medicinal product(s)

See IB for more details. MSTT1041A (anti-ST2) is a first-in-class, fully human, IgG2 monoclonal antibody (mAb) being developed for use in the treatment of asthma and COPD. Anti-ST2 binds with high affinity to the human receptor for IL-33/ST2, and blocks IL-33 binding, thus inhibiting association with the IL-1R accessory protein (AcP) co-receptor and formation of an activated receptor complex.

Anti-ST2 is presented as sterile, clear, and colourless to slightly yellow liquid. Each sterile vial is filled with a 1 mL deliverable volume of 70 mg/mL. It is formulated with 15 mM sodium acetate, 9.0% (w/v) sucrose, 0.01% (w/v) polysorbate 20, pH 5.2.

Placebo for Anti-ST2 (MSTT1041A) is formulated with 10 mM sodium acetate, 9.0% (w/v) sucrose, 0.004% (w/v) polysorbate 20, pH 5.2, and is supplied in an identical vial configuration.

8.2 Regulatory status of the drug

Anti-ST2 is currently in development and has not been granted marketing approval in any country yet. The drug and placebo will be supplied by Genentech, South San Francisco, California, USA.

8.3 **Product Characteristics**

See Investigator's Brochure (IB).

8.4 Drug storage and supply

The Anti-ST2 and placebo will be supplied by Genentech free of charge. They will be provided as open-label product to unblinded pharmacist and trial staff. Unblinded staff will be responsible for the receipt, storage, and labelling.

Both the Anti-ST2 (MSTT1041A) and Placebo should be stored at 2°C to 8°C in a secured location, protected from light, and according to the storage and expiration information (where required) provided on the label that is affixed to the package containing the investigational product(s). The drug product(s) should not be shaken.

The Anti-ST2 and placebo contain no preservatives and are suitable for single use only. Anti-ST2 should be prepared per the instructions provided in the Pharmacy Guide or trial drug preparation instructions. Vials should be checked for cracks or damage that may have occurred. Damaged product should not be administered and should be returned to Genentech. Any temperature deviations will be recorded and reported for evaluation to Genentech, LCTU and the Sponsor. Stock that has been exposed to a temperature deviation will be quarantined at

Page 23 of 60

the correct temperature pending Genentech's response on outcome and authorisation from the Sponsor to use or destroy the affected stock.

